#### 4.7.1.1. Adverse Events and Serious Adverse Events

Adverse events (including serious adverse events (SAE), AEs causing permanent treatment discontinuation, deaths, and AEs of special interest) are recorded from the time of signed informed consent until the end of study. All AEs diagnosed by the Investigator will be reported and described.

All AEs will be dictionary coded by “lowest level term (LLT)”, “preferred term (PT)”, “high level term (HLT)”, “high level group term (HLGT)” and associated primary “system organ class (SOC)” using the version of MedDRA in effect at the time of database lock for the analysis.

#### *Adverse Event Observation Period*

- Pre-treatment AEs are AEs that developed or worsened or became serious during the pre-treatment period.

- Double-Blind and open-label treatment-emergent adverse events are AEs that developed or worsened or became serious during the respective TEAE period.
- Double-Blind and open-label post-treatment AEs are AEs that developed or worsened or became serious during the post-treatment period.

#### 4.7.1.2. Adverse Events of Special Interest

Adverse events of special interest (AESI) are AEs (serious or non-serious) required to be monitored, documented, and managed in a pre-specified manner as described in the protocol. In this study, AESI are the following (their complete descriptions are provided in the protocol):

- Local injection site reactions, selected using an e-CRF specific tick box on the AE page;
- Allergic events:
  - General allergic events will be tabulated. Events will be selected using standardized MedDRA query (SMQ) “hypersensitivity” (broad and narrow) excluding the following preferred terms linked to local injection site reactions (“infusion site dermatitis”, “infusion site hypersensitivity”, “infusion site rash”, “infusion site urticaria”, “infusion site eczema”, “infusion site vasculitis”, “infusion site photosensitivity reaction”, “infusion site recall reaction”, “injection site dermatitis”, “injection site hypersensitivity”, “injection site rash”, “injection site urticaria”, “injection site eczema”, “injection site vasculitis”, “injection site photosensitivity reaction”, and “injection site recall reaction”);
- ALT  $\geq 3$  ULN in the case baseline ALT < ULN or ALT  $\geq 2$  times the baseline value in the case baseline ALT  $\geq$  ULN, selected using laboratory data;
- Neurologic events selected using SMQs “demyelination” (broad and narrow), “peripheral neuropathy” (broad and narrow), and “Guillain-Barre syndrome” (broad and narrow) excluding the following preferred terms: “acute respiratory distress syndrome”, “asthenia”, “respiratory arrest” and “respiratory failure” and including selected PTs from SMQ “optic nerve disorders” (see [Appendix 10.5 Table 3](#) for the list of terms)
- Symptomatic overdose with investigational medicine product, selected using HLT “Overdose” and the tick box “Symptomatic Overdose” in the e-CRF AE page.
- Pregnancy of female patient/subject (including male subject’s partner), selected using appropriate MedDRA codes.
- Neurocognitive events:

- Selected using a company MedDRA query (CMQ), based on the following 5 HLGTs: “deliria (including confusion)”, “cognitive and attention disorders and disturbances”, “dementia and amnestic conditions”, “disturbances in thinking and perception”, and “mental impairment disorders”.
- A second grouping of terms for neurocognitive events was defined based on Regulatory Agency request (see [Appendix 10.5 Table 4](#) for the list of terms)
- Cataract using HLT “Cataract conditions”

In addition, the following grouping of events will be provided:

- Hepatic disorder events using SMQ “Hepatic disorder”
- Diabetes mellitus or diabetic complications using HLGT “diabetes complications” (including PTs pertaining to the secondary SOC included in the HLGT), HLT “diabetes mellitus”, and HLT “carbohydrate tolerance analyses (incl diabetes)” excluding PTs “blood glucose decreased” and “Glycosylated haemoglobin decreased” and including the PTs “hyperglycaemia”, “Hyperglycaemic unconsciousness” and “Hyperglycaemic seizure” from the HLT “Hyperglycaemic conditions NEC”

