### 9.3.3. Adverse Events of Special Interest

An adverse event of special interest (serious or non-serious) is one of scientific and medical concern specific to the sponsor's product or program, for which ongoing monitoring and rapid communication by the investigator to the sponsor can be appropriate. Such an event might warrant further investigation in order to characterize and understand it. Depending on the nature of the event, rapid communication by the trial sponsor to other parties (e.g., regulators) might also be warranted (Section 9.4.3).

Adverse events of special interest for this study include the following:

- Increase in ALT: ALT  $\geq 3 \times$  ULN (if baseline ALT  $<$  ULN), or ALT  $\geq 2$  times the baseline value (if baseline ALT  $\geq$  ULN)
- Allergic events and/or local injection site reactions that require consultation with another physician for further evaluation
- Pregnancy
- Symptomatic overdose with investigational medicinal product
- Neurologic events that require additional examinations/procedures and/or referral to a specialist
- Neurocognitive events
- Cataracts
- New onset of diabetes

The definition of new onset of diabetes (NOD) will be the following:

- Type 1 or type 2 diabetes TEAE (grouping of Medical Dictionary for Regulatory Activities [MedDRA®] terms will be specified in the SAP)

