#### ***Analysis of groupings of adverse events including selected adverse events of special interest***

- All grouping of TEAEs including adverse events of special interest, as listed in [Section 4.7.1.2](#), will be presented by SMQ/CMQ and PT (when selection is based on SMQs/CMQs) and by SOC and PT (when selection is based on the e-CRF tick box or HLT/HLT). The summaries will be sorted by decreasing incidence of PT within each SOC/SMQ (in the alirocumab group).
- All TEAEs within diabetes grouping will be analyzed overall and according to the diabetic status at baseline.

The following variables will also be tabulated for the local injection site reactions TEAEs:

- Intensity of the event (mild, moderate, severe);
- Number of events divided by the number of double-blind study treatment injections received;

- Time from first study treatment injection (double-blind or open-label depending on the analysis) to first injection site reaction;
- Description of the highest intensity of each symptom recorded in the specific e-CRF page with table and bar chart.

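### The SAP presents unconditioned groupings as the AESIs for allergic, injection-site and neurologic events, and no planned table shows the events that meet the protocol's definition

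*SAP*

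**What the plan says.** Protocol 9.3.3 attaches a condition to three kinds of event. Two share one entry: "Allergic events and/or local injection site reactions that require consultation with another physician for further evaluation". The third is "Neurologic events that require additional examinations/procedures and/or referral to a specialist". Protocol 9.4.3 makes every AESI, serious or not, reportable to the sponsor within 24 hours.

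SAP 4.7.1.2 opens its list with "In this study, AESI are the following (their complete descriptions are provided in the protocol" and then gives a selection rule for each kind:

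- Injection-site reactions: "Local injection site reactions, selected using an e-CRF specific tick box on the AE page".
- Allergic events: "General allergic events will be tabulated", using the hypersensitivity query (broad and narrow) less a list of site-reaction terms.
- Neurologic events: "Neurologic events selected using SMQs" for demyelination, peripheral neuropathy and Guillain-Barre syndrome, less four preferred terms, plus the optic-nerve terms in Appendix 10.5.

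SAP 5.7.1 builds the tables from that list: "All grouping of TEAEs including adverse events of special interest, as listed in" Section 4.7.1.2. SAP 1.2.3 declares a single modification from Protocol Amendment 3, which concerns new onset of diabetes.

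**The concern.** The two documents use one label for different sets of events. The protocol picks out events by what they led to: a consultation, a work-up or a referral. The SAP picks them out by how they were coded or by a box on the adverse event page. A reader of the clinical study report would take a row presented as an AESI to hold the events defined in the protocol, and it need not.

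What is at stake is whether the events the protocol singled out can be read by treatment arm. A neurologic event that was referred and reported as an AESI, but coded outside the listed terms, would not be in the AESI table. The 24-hour AESI reports also need not agree with the AESI tables, and nothing in the SAP would tell the reader why.

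**Working it through.** No sample size, power or error rate depends on this point, so the check is a comparison of the two definitions.

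| Event | Condition in Protocol 9.3.3 | Selection in SAP 4.7.1.2 | SAP set relative to protocol set |
|---|---|---|---|
| Allergic | Another physician consulted | Hypersensitivity query less site terms | Wider: counts events with no consultation |
| Neurologic | Further work-up or referral | Three queries less four terms, plus optic-nerve terms | Differs both ways: counts listed terms with no work-up, omits referred events coded elsewhere |
| Injection-site | Another physician consulted | Tick box, content not shown | Probably wider |

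**Neurologic omission.** Asthenia is one of the four preferred terms removed from the neurologic queries. A patient referred to a specialist whose event was coded to that term would meet the protocol's definition and be absent from the SAP's neurologic table.

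**Injection-site reactions.** SAP 5.7.1 plans intensity, events per injection, time to first reaction and symptom descriptions for these events. Such outputs suit a set of all local reactions. That is an inference, because neither document says what the tick box records.

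**Are qualifiers dropped throughout the list?** No. The ALT entry keeps the protocol's baseline-dependent thresholds. The overdose entry combines a MedDRA term with a box for symptomatic cases, so that qualifier survives. Only the consultation, work-up and referral conditions are missing.

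**Does the SAP separate AESIs from other groupings?** Yes. After the AESI list, SAP 4.7.1.2 adds hepatic and diabetes events as further groupings. The unconditioned allergic, injection-site and neurologic sets stand above that line, among the AESIs.

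**Is the difference declared?** No. The one declared change is itself to an item in Protocol 9.3.3, so the sponsor treated a change of this kind as one to list.

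**Size.** The share *f* of events meeting the protocol's condition is not given. If the SAP set contains the protocol set, the ratio of the two counts is 1/*f*. Assumed values of 50%, 25% and 10% give 2, 4 and 10, whatever the event rate, so the ratio only restates the assumption.

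A rough idea of how sparse a protocol-defined row might be comes from the product-label injection-site rate of 7.2% on alirocumab quoted in Protocol 3.2.2. With 74 × 2/3, or about 49 patients, on alirocumab, 49 × 0.072 = 3.5 patients would have any reaction. The same assumed shares leave 1.8, 0.9 and 0.4 patients. That rate is not from this trial, and the documents offer no corresponding basis for allergic or neurologic events.

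**The case against.** The strongest reply is that the two definitions do different jobs. Protocol 9.3.3 and 9.4.3 set a threshold for rapid reporting by sites. Protocol Section 10 is the basis for the SAP, and 10.4.4.1 provides for tables of events of interest defined by a preferred term or a pre-specified grouping. The SAP supplies those tables, its selection is visible in advance, and the heading in SAP 5.7.1 already speaks of groupings. For allergic and injection-site events, a wider set is also cautious and does not depend on local referral habits.

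Most of this stands. The groupings are permitted and useful. It does not meet the remaining point: SAP 4.7.1.2 says that these sets are the AESIs and refers to the protocol for their full description, yet does not apply that description. Nor does any planned table show the protocol-defined events.

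Three stronger readings are tempting and not supported:

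- **An AESI rate inflated 2 to 10 times, or swamped by ordinary reactions.** No pooled AESI rate is planned. SAP 5.7.1 shows each grouping separately, and the multiple is just 1/*f* for assumed shares.
- **Every injection-site reaction is certainly counted.** The tick box's content is not shown.
- **Events are lost from safety reporting.** A treatment-emergent event outside the neurologic list still appears in the all-TEAE tables.

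**Conclusion.** There is a real and undeclared mismatch of definition. It is certain on the text for allergic and neurologic events, and probable for injection-site reactions. The neurologic part matters most, because that grouping can omit events the protocol asked sites to report quickly as well as include events it did not.

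The consequence is modest. Safety summaries are descriptive under Protocol 10.4.4 and SAP 5.7, and no efficacy conclusion is touched. The numerical effect cannot be estimated from the documents. The conclusion assumes that the SAP's selection rules will be programmed as written, with the reference to the protocol's descriptions not acting as a further filter.

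**What to change.** 1. In SAP 4.7.1.2 and 5.7.1, keep the query-based and tick-box tables for these three kinds of event, but label them as groupings of treatment-emergent events of interest, as is already done for hepatic and diabetes events.
2. Add one table or listing, by arm, of the AESIs that investigators reported under Protocol 9.3.3 and 9.4.3, whatever their preferred term. Take these from an e-CRF flag if one exists, and otherwise from the 24-hour reports.
3. State in SAP 1.2.3 that the groupings differ from the protocol's AESI definition, and say what the injection-site tick box records.

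The cost is SAP wording and one additional output that will probably hold few patients. The documents show no AESI flag and no consultation or referral field in the e-CRF. Protocol 11.2 lists the pharmacovigilance database separately from data capture, so the added output may need a reconciliation between the two. Trial conduct, endpoints and sample size do not change.

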#### 4.7.1.3. Events Causing Death

The observation periods for patient deaths are per the observation periods defined above.

- Death on-treatment: deaths occurring during the respective TEAE period (double-blind or open-label),
- Death post-treatment: deaths occurring during the respective post-treatment period (double-blind or open-label).

#### 4.7.2. Clinical Laboratory Safety Variables

Clinical laboratory tests will consist of blood analyses (including hematology and clinical chemistry) and urinalysis. Clinical laboratory values will be converted and analyzed in international units, including associated normal ranges provided by the central laboratory. International units will be used in all listings and tables. Clinical laboratory values in conventional (US) units will also be available in the database, with associated normal ranges (analyses can be provided upon request). Both actual test values and “change from baseline” values (defined as the post-baseline value minus the baseline value) will be used in the result summaries. Potentially clinically significant abnormalities (PCSA) ranges will be applied to the laboratory test values as applicable (see [Appendix 10.3](#) for PCSA definitions).

Unless otherwise specified below, blood samples for clinical laboratories will be collected at week -2, week 0, and weeks 8, 12/or end of double-blind treatment visit, and week 24/or end of

open-label treatment visit. The laboratory parameters (excluding those considered as efficacy parameters) will be classified as follows:

- Hematology:
  - Red blood cells and platelets: hemoglobin, hematocrit, erythrocytes count, platelets count, reticulocyte count, red blood cell distribution width (RDW)
  - White blood cells: white blood cell count, neutrophils, lymphocytes, monocytes, basophils, eosinophils
- Clinical chemistry:
  - Metabolism: glucose, total protein, albumin, creatine phosphokinase
  - Electrolytes: sodium, potassium, chloride, calcium, phosphorus, bicarbonate
  - Renal function: creatinine, creatinine clearance, blood urea nitrogen, uric acid
  - Liver function ALT, aspartate aminotransferases (AST), alkaline phosphatase (ALP), total bilirubin, LDH
- Hepatitis screen: anti-hepatitis-C antibody collected at week -2 and week 12, and hepatitis B surface antigen collected at week -2

#### **4.7.3. Vital Sign Variables**

Vital signs parameters will include weight (kg), heart rate (bpm), systolic and diastolic blood pressure (mmHg) in a sitting position for at least five minutes (arm used for blood pressure measurement is also collected). Both actual test values and “change from baseline” values (defined as the post-baseline value minus the baseline value) will be used in the result summaries. Potentially clinically significant abnormalities (PCSA) ranges will be applied to the vital sign parameter values as applicable (see [Appendix 10.3](#) for PCSA definitions).

#### **4.7.4. Electrocardiogram Variables**

Electrocardiograms were recorded automatically by the device at the Investigator site at week -2, week 12/or end of double-blind treatment visit, and week 24/or end of open-label treatment visit. Electrocardiogram assessments will be described as normal or abnormal.

### **4.8. Other Variables**

Other assessment endpoints are listed and defined below. As applicable, LDL-C will use the same definition as described in [Section 4.6.1](#).

- The percent change in hs-CRP from baseline to weeks 12, and 24. Hs-CRP values greater or equal to 10 mg/L will be excluded from analyses in a second approach, since these are suggestive of concurrent infections (1). PCSA (potentially clinically significant abnormalities) criteria for hs-CRP are listed in [Appendix 10.3](#).
- The proportion of patients with two consecutive results, separated by at least 21 days, of LDL-C <25 mg/dL (<0.65 mmol/L) (and again for LDL-C <15 mg/dL [< 0.39 mmol/L]) during the double-blind period.
- The proportion of patients with two consecutive results, separated by at least 21 days, of LDL-C <25 mg/dL (<0.65 mmol/L) (and again for LDL-C <15 mg/dL [< 0.39 mmol/L]) during the open-label period.
- For the patients with two consecutive results as described above, the time to the first LDL-C <25 mg/dL (<0.65 mmol/L) (and again for LDL-C <15 mg/dL [< 0.39 mmol/L]) during the respective treatment period (double-blind or open-label).
- The change in the proportion of patients who meet US apheresis eligibility criteria from baseline to week 12 ([Goldberg 2011](#)) (7).
  - A patient is considered as meeting US apheresis eligibility criteria if LDL-C  $\geq$  300 mg/dL (7.77 mmol/L).
- The change in the proportion of patients who meet German apheresis eligibility criteria from baseline to week 12 ([Schettler 2012](#)) (8).
  - A patient with primary CVD prevention is considered as meeting German apheresis eligibility criteria if LDL-C > 160 mg/dL (4.2 mmol/L).
  - A patient with secondary CVD prevention is considered as meeting German apheresis eligibility criteria if LDL-C > 120 mg/dL (3.1 mmol/L).
- Exploratory relationships between HoFH genotype status and lipid parameters.

#### 4.9. Anti-alirocumab Anti-body Variables

Anti-drug (alirocumab) antibody (ADA) are assessed at baseline (before the first study treatment injection), at week 12/or end of double-blind treatment visit, and week 24/or end of open-label treatment visit. ADA measurements will be assigned to similar analysis windows as defined for efficacy endpoints in [Appendix 10.2](#). As appropriate, patient frequencies and percentages will be depicted, and the percentages will be calculated based on the ADA population for the analysis of the double-blind period and based on the OLE population for the analysis of the open-label period.

The following variables will be described:

- ADA response (Positive or Negative). For ADA positive:
  - Titer levels
  - Neutralizing status (Positive or Negative)
- Pre-existing positive ADA defined as patients with positive ADA response at baseline with less than 4-fold increase in titer in the post-baseline period
- Treatment-emergent positive ADA response defined as 1) Patients with no ADA positive response at baseline but with any positive response in the post-baseline period or 2) Patients with a positive ADA response at baseline and at least a 4-fold increase in titer in the post-baseline period. For treatment-emergent positive ADA, the following categories for ADA duration will be applied for the analysis of the double-blind period:
  - A persistent positive response is a treatment-emergent ADA positive response detected in at least 2 consecutive post-baseline samples separated by at least a 12-week period
  - An indeterminate duration positive response is defined as ADA present only at the last sampling time point
  - A transient positive response is defined as any treatment-emergent positive ADA response that is neither considered persistent nor indeterminate

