### 3.3. The Anti-alirocumab Antibody Analysis Set

The anti-alirocumab antibody analysis of the double-blind period will be performed on all randomized and treated patients (safety population) with a sample at week 0 (baseline) and at least 1 evaluable sample for anti-alirocumab antibodies after the first dose of double-blind study treatment (ADA population).

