### **3.6. The Open-Label Analysis Set**

For the open-label period, the open-label analysis population for all measurements (efficacy, safety, quality of life, PK and ADA) will be defined as those patients who received at least 1 dose or part of a dose of open-label investigational study drug alirocumab.

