### ***General common rules***

All safety analyses will be performed, unless otherwise specified, using the following common rules:

- Safety data in patients who do not belong to the safety population (i.e., exposed but not randomized) will be listed separately.
- For the analyses of both double-blind and open-label periods, the baseline value is defined as the last available value obtained up to the date and time of the first double-blind study treatment, except otherwise specified.
- PCSA values are defined as abnormal values considered medically important by the Sponsor according to predefined criteria/thresholds based on literature review and defined by the Sponsor for clinical laboratory tests and vital signs (PCSA version dated January 2009 [\[Appendix 10.3\]](#)). Considering that the threshold defined in the PCSA list for monocytes and basophils can be below the ULN, the following PCSA criterion will be used for the PCSA analysis of monocytes and basophils:
  - PCSA criterion for monocytes:  $>0.7$  Giga/L or  $>\text{ULN}$  (if  $\text{ULN} \geq 0.7$  Giga/L).
  - PCSA criterion for basophils:  $>0.1$  Giga/L or  $>\text{ULN}$  (if  $\text{ULN} \geq 0.1$  Giga/L).
- PCSA criteria will determine which patients had at least 1 PCSA during the TEAE period, taking into account all evaluations including nonscheduled or repeated evaluations.
- The treatment-emergent PCSA denominator by treatment group for a given parameter will be based on the number of patients assessed for that given parameter at least once during the TEAE period.
- All measurements, scheduled or unscheduled, fasting or not fasting, will be assigned to analysis windows defined in [Appendix 10.2](#), [Table 1](#) and [Table 2](#) in order to provide an assessment for week 4 to week 24 time points.
- For quantitative safety parameters including central laboratory measurements and vital sign scores, descriptive statistics will be used to summarize results and change from baseline values by visit, the last on-treatment value and the worst on-treatment value. The last on-treatment value is defined as the last post-baseline value collected during the respective treatment period (as defined in [Section 4.7.1](#)). The worst on-treatment value is defined post-baseline as the nadir and/or the peak value collected during the respective treatment period, according to the direction (minimum or maximum) of the abnormality as defined in the PCSA list.

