#### 5.9. Analysis of Anti-alirocumab Antibody Variables

The summary of ADA variables will be presented separately for the double-blind and open-label period. The double-blind period will be presented by treatment groups (alirocumab, placebo) on the ADA population. The open-label period will be presented by all patients and by treatment group of the double-blind period (i.e., alirocumab, placebo) on the open-label population. No

formal inferential testing will be performed for either period. Summaries will be descriptive in nature.

ADA variables will be summarized, taking into account all samples regardless of timing in relation to injections. ADA results will be summarized as follows:

- ADA results (negative or positive) by time point
- Neutralizing status (negative or positive) by time point for positive ADA
- ADA titers using descriptive statistics (median, minimum and maximum) for positive ADA by time point
- Number (%) of patients with pre-existing ADA and number (%) of patients with treatment-emergent ADA positive response
- Number (%) of patients with persistent/indeterminate/transient treatment-emergent ADA positive response (only for the double-blind period)
- Time to onset of treatment-emergent ADA positive response using descriptive statistics.

Correlations between ADA parameters (e.g., titers, treatment-emergent ADA positive status, neutralizing status) and safety and/or efficacy endpoints will also be explored (e.g., scatter plot).

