### 6.1. Definition of Baseline for Efficacy and Safety Variables

Unless otherwise specified, the baseline assessment is programmatically defined as the latest available measurement taken before first administration of double-blind study treatment. For patients randomized but not-treated, the baseline will be the last available measurement before randomization.

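### Open-label ADA table: ex-placebo patients are judged against Week 0, so antibody changes that arose on placebo can count as treatment-emergent, and the percentage base requires no ADA sample

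*SAP*

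**What the plan says.** **Baseline.** SAP 4.9 places the ADA baseline before the first study injection and schedules later samples at Week 12 and Week 24, or at the corresponding end-of-treatment visits. SAP 6.1 sets the general default as "the latest available measurement taken before first administration of double-blind study treatment". The common rules in SAP 5.7 state for both study periods that "the baseline value is defined as the last available value obtained up to the date and time of the first double-blind study treatment". Both defaults yield to a different specification, but none is given for ADA in ex-placebo patients.

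**Definition.** One route to a treatment-emergent response in SAP 4.9 is "Patients with no ADA positive response at baseline but with any positive response in the post-baseline period". The other is a positive baseline followed by a titre rise of at least fourfold.

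**Timing of the Week 12 sample.** Every patient starts open-label alirocumab at Week 12 (protocol 5.1). On dosing days, ADA blood is drawn before study drug (protocol 8.1.1, footnote 6). SAP Appendix 10.2, Table 1a, puts that sample in the double-blind window, which closes at the first open-label injection.

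**Percentage base.** SAP 4.9 bases ADA percentages "based on the ADA population for the analysis of the double-blind period and based on the OLE population for the analysis of the open-label period". Members of the double-blind ADA set are treated patients "with a sample at week 0 (baseline) and at least 1 evaluable sample for anti-alirocumab antibodies" after the first double-blind dose (SAP 3.3). The open-label set is "those patients who received at least 1 dose or part of a dose of open-label investigational study drug alirocumab" (SAP 3.6, following protocol 10.3.3). SAP 6.4 leaves patients with missing data out of percentages for categorical variables unless something else is specified.

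**Display.** SAP 5.9: "The open-label period will be presented by all patients and by treatment group of the double-blind period". ADA status and titre are also shown by time point. No formal testing is planned.

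**The concern.** For patients randomised to alirocumab, Week 0 is the last sample before any alirocumab. For patients randomised to placebo, that sample is Week 12. Using Week 0 for both means that the open-label interval for ex-placebo patients contains 12 weeks on placebo, and an antibody change in those weeks enters the open-label count.

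The development of ADA is a stated secondary objective (protocol 2.2, SAP 1.2.2). The ex-placebo open-label column describes 12 weeks of first exposure, so readers will naturally set it beside the double-blind alirocumab column. As written, the two differ in what precedes the interval and in who is in the denominator.

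**Working it through.** The documents give no expected ADA rate or count, so there is no plan figure to reproduce. The check traces the definitions and then shows the scale.

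**1. Two ex-placebo patients under the stated rules** (T is any positive titre)

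| Sample | Relation to alirocumab | Patient A | Patient B |
|---|---|---|---|
| Week 0 | before any | negative | positive, T |
| Week 12 | before the first dose | positive, T | positive, 4T |
| Week 24 | after 12 weeks | positive, T | positive, 4T |

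- Against Week 0, A goes from negative to positive and B has 4T/T = 4. Both are treatment-emergent.
- Against the last sample before alirocumab, A has T/T = 1 and B has 4T/4T = 1. Neither is treatment-emergent.

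SAP 4.9 does not define the post-baseline period for the open-label table. A patient positive at Week 12 only is therefore not clearly counted, and the finding is confined to changes still present at Week 24.

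The SAP does reset the clock elsewhere. Appendix 10.2, Table 2, counts open-label days from the first open-label injection, and SAP 5.7.1 times injection-site reactions from the first injection of the period analysed. ADA has no such reset.

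**2. Size per case**

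Inputs: about 74 patients, 2:1 (SAP 2.1), and all assumed to enter the open-label period.

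- Ex-placebo: 74 × 1/3 = 24.7, about 25. Ex-alirocumab: 74 − 25 = 49.
- One case: 1/25 = 4.0 points in the ex-placebo column; 1/74 = 1.35, about 1.4 points overall.
- Two cases: 2/25 = 8.0 points; 2/74 = 2.7 points.
- With the last pre-alirocumab sample as baseline, the contribution is 0 unless the titre then rises at least fourfold.

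Frequency is an assumption. If a share q of placebo patients converts by Week 12, the expected number is 25q and the chance of at least one is 1 − (1 − q)^25:

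| q (assumed) | Expected converters | Chance of at least one |
|---|---|---|
| 1% | 0.25 | 22% |
| 2% | 0.50 | 40% |
| 5% | 1.25 | 72% |

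These are upper bounds on misattributed cases at each q, because a converter must also enter the open-label period and still be positive at Week 24.

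**3. Percentage base**

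If a share u of open-label patients has no open-label ADA result and stays in the denominator, the reported rate is the rate among sampled patients × (1 − u). For an assumed 8%:

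- u = 5%: 8% × 0.95 = 7.6%
- u = 10%: 8% × 0.90 = 7.2%
- u = 20%: 8% × 0.80 = 6.4%

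If SAP 6.4 removes those patients, the dilution is 0. The documents do not give u. The only related figure is the 5% non-evaluable rate in SAP 2.2, and that concerns the primary endpoint.

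The open-label set also requires no Week 0 sample. Read literally, a patient with a missing baseline has no positive response at baseline, so a later positive could be counted. SAP 3.3 prevents this only in the double-blind analysis.

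**The case against.** **Baseline.** A single study baseline for both periods is a stated and consistent convention, used for efficacy (SAP 5.6) and safety (SAP 5.7). Double-blind results by arm show conversions on placebo, and results by time point show which ex-placebo patients were positive before alirocumab. The controlled double-blind comparison addresses the secondary objective, and its baseline is not in question. No comparison of open-label with double-blind ADA columns is planned. All of this stands and limits the importance of the point. It does not correct the treatment-emergent count, which remains wrong for any patient like A or B.

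A reader might go further and infer that such cases are reported as alirocumab-induced. The SAP does not use that term. Its category is treatment-emergent relative to study baseline, so the fault is a misplaced count in an alirocumab-only period, not a stated causal claim.

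**Percentage base.** A reader might also infer that patients who leave before Week 24 are counted as negative and certainly dilute the rate. The documents do not establish this:

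- SAP 4.9 allows the end-of-open-label visit in place of Week 24. Protocol 7.4.2 and 8.1.2 ask patients who stop early to have those assessments, within 5 days if possible, and SAP 5.9 accepts samples whatever their timing relative to injections.
- SAP 6.4 normally drops missing data, and naming an analysis population is not clearly an exception to that rule.

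What remains is an ambiguity with two possible published rates. It would matter most if open-label ADA were reported at the first-step analysis, whose cut-off is the last Week 12 visit (SAP 7), when recent entrants could not yet have a Week 24 sample. The SAP does not say that ADA will be reported then.

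**Conclusion.** The baseline point holds. Under SAP 4.9, with the defaults in 5.7 and 6.1, a change that arose on placebo and persists at Week 24 is tabulated as treatment-emergent in the open-label period. SAP 5.7 is written for safety analyses and ADA has its own section, but 4.9 and 6.1 lead to the same result.

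Each case is worth about 4 points in a column of about 25 and about 1.4 points overall. This assumes the planned 74 patients at 2:1 and near-complete entry to the open-label period. The frequency of such cases cannot be taken from the documents.

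The denominator point holds as an inconsistency with the double-blind set and an unresolved reading of SAP 6.4; dilution is possible, not shown. Both points concern descriptive tables. The primary analysis and the sample size are untouched.

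**What to change.** In SAP 4.9 and 5.9:

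- **Baseline.** For ex-placebo patients, define the open-label ADA baseline as the last sample before the first open-label injection, and count only samples after that injection as post-baseline. Keep Week 0 for ex-alirocumab patients and label their column as cumulative.
- **Percentage base.** Base open-label treatment-emergent percentages on open-label patients who have the relevant baseline and at least one evaluable ADA sample after the first open-label injection. List this in SAP 1.2.3 as a change from protocol 10.3.3, which sets the open-label population for ADA.

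No new blood is needed, because the Week 12 sample is already scheduled before dosing. The cost is a small derivation change, a possibly slightly smaller denominator, and an ADA baseline for ex-placebo patients that departs from the single-baseline convention used elsewhere, which a table footnote should state.
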